## 1. VERSION HISTORY

This Statistical Analysis Plan (SAP) for study B9991027 is based on the protocol amendment 1 dated 07MAR2018 and Protocol Administrative Change Letters dated 01JUN2018 and 14DEC2018.

CCI

CCI

CCI

## 2. INTRODUCTION

This SAP provides the detailed methodology for summary and statistical analyses of the data collected in study B9991027. This document may modify the plans outlined in the protocol; however, any major modifications of the primary endpoint definition or its analysis will also be reflected in a protocol amendment.

Statistical analyses will be performed using cleaned eCRF data as well as non-CRF data (ie, pharmacokinetics data, immunogenicity data, and biomarker data). The primary (also the final) analysis of the data will be performed after last patient last visit (LPLV).

Additional analyses of the data may be performed for publication or regulatory reporting purposes.

### 2.1. Study Objectives

#### Primary Objective

To evaluate the Objective Response Rate (ORR) based on Investigator assessment, per Response Evaluation Criteria in Solid Tumors (RECIST) version (v) 1.1 of avelumab in combination with axitinib in patients with advanced or metastatic non-small cell lung cancer (NSCLC) who have received at least one prior platinum-containing therapy and in treatment naïve patients with advanced or metastatic urothelial cancer (UC), who are ineligible for cisplatin-containing chemotherapy for their advanced disease.

#### Secondary Objectives

To evaluate the following in patients with advanced or metastatic NSCLC who have received at least one prior platinum-containing therapy and in treatment naïve patients with advanced or metastatic UC, who are ineligible for cisplatin-containing chemotherapy for their advanced disease:

- The safety and tolerability of avelumab in combination with axitinib;
- The anti-tumor activity of avelumab in combination with axitinib;
- The pharmacokinetics (PK) of avelumab and axitinib when administered in combination;
- Candidate predictive and/or early response biomarkers in pre-treatment tumor tissue and pre- and post-treatment blood samples that may aid in the identification of a patient subpopulation most likely to benefit from treatment with avelumab in combination with axitinib. Assessments may include but are not limited to tumor mutational burden, immune repertoire and PD-L1 expression within the tumor microenvironment;
- The immunogenicity of avelumab when combined with axitinib.

CCI

[figure not shown]
## 2.2. Study Design

This is an open-label, multi-center, Phase 2 study to evaluate the safety and efficacy of avelumab in combination with axitinib in patients with advanced or metastatic NSCLC who have received at least one prior platinum-containing therapy, and in patients with advanced or metastatic UC, who are treatment naïve and ineligible for cisplatin-containing chemotherapy for their advanced disease.

Patients will receive avelumab 800 mg intravenous (IV) every 2 weeks (Q2W) on Days 1 and 15 of each 28-day cycle in combination with axitinib 5 mg by mouth (PO) twice daily (BID) on a continuous dosing schedule.

Approximately 40 patients will be enrolled in each cohort, NSCLC and UC (Figure 1).

**Figure 1. Study Design Schema**

## 3. ENDPOINTS AND BASELINE VARIABLES: DEFINITIONS AND CONVENTIONS

### 3.1. Primary Endpoint

- Confirmed Objective Response (OR) based on Investigator assessment per RECIST v1.1. OR is defined as complete response (CR) or partial response (PR) according to RECIST v1.1 from the date of first dose of study treatment until the date of the first documentation

of progressive disease (PD). Both CR and PR must be confirmed by repeat assessments performed no less than 4 weeks after the criteria for response are first met.

### 3.2. Secondary Endpoints

#### 3.2.1. Safety endpoints

- Adverse events (AEs) as characterized by type, severity as graded by National Cancer Institute [NCI] Common Terminology Criteria for Adverse Events [CTCAE] v4.03, timing, seriousness, and relationship to study treatments;

AEs will be graded by the investigator according to the CTCAE v4.03 and coded using the Medical Dictionary for Regulatory Activities (MedDRA)

- Laboratory abnormalities as characterized by type, severity (as graded by NCI CTCAE v4.03) and timing.

#### 3.2.2. Efficacy endpoints

- Time-to-event endpoints including time to tumor response (TTR), duration of response (DR), progression-free survival (PFS) based on Investigator assessment per RECIST v1.1, and overall survival (OS).

DR is defined, for patients with OR, as the time from the first documentation of objective response (CR or PR) to the date of first documentation of PD or death due to any cause.

TTR is defined, for patients with an OR, as the time from the date of first dose of study treatment to the first documentation of objective response (CR or PR) which is subsequently confirmed.

PFS is defined as the time from the date of first dose of study treatment to the date of the first documentation of PD or death due to any cause, whichever occurs first.

OS is defined as the time from the date of first dose of study treatment to the date of death due to any cause.

#### 3.2.3. Pharmacokinetic endpoints

- Pharmacokinetic parameters including trough and maximum concentrations ( $C_{trough}$ ,  $C_{max}$ ) of avelumab and axitinib.

Pharmacokinetic parameters ( $C_{max}$  and  $C_{trough}$  after single dose and at steady state).

**Table 2. PK Parameters to be Determined for Avelumab and Axitinib**

Parameter	Definition	Method of Determination
$C_{max}$	Maximum observed plasma concentration	Observed directly from data
$C_{trough}$	Pre-dose observed plasma concentration	Observed directly from data
$C_{max}(dn)$	Dose normalized $C_{max}$ for axitinib	$C_{max} / Dose$
$C_{trough}(dn)$	Dose normalized $C_{trough}$ for axitinib	$C_{trough} / Dose$

### 3.2.4. Immunogenicity endpoints

- Anti-drug antibody (ADA) titers and neutralizing antibodies (nAb) against avelumab.

[figure not shown]
### 3.2.5. Biomarker endpoints

- Tumor tissue biomarker status (ie, positive or negative based on, for example, PD-L1 expression and/or quantitation of tumor mutational burden as well as characterization of the immune repertoire in peripheral blood and/or tumor).

**Table 3. Biomarker Definition and Determination**

Parameter	Definition	Method of Determination
PD-L1 expression	Assessment of the proportion (%) of tumor cells and immune cells displaying PD-L1 staining of any intensity within the tumor microenvironment	Pathologist, assisted by image analysis
Immune repertoire	Determination of the identity and abundance of individual T cell clones in peripheral blood and/or tumor tissue samples at baseline and on-treatment	TCR sequencing
Tumor mutational burden	Determination/estimation of the frequency of mutations (total and non-synonymous) present in baseline tumor derived nucleic acid samples	Whole exome or genome sequencing and/or RNAseq

CCI

## 3.4. Baseline Variables

### 3.4.1. Study drug, study treatment and baseline definitions

In this study, ‘**study drug**’ refers to avelumab or axitinib and ‘**study treatment**’ (or ‘**treatment group**’) refers to one of the following:

- NSCLC Cohort: avelumab 800 mg IV Q2W plus axitinib 5 mg PO BID;
- UC Cohort: avelumab 800 mg IV Q2W plus axitinib 5 mg PO BID.

### Start and end dates of study treatment:

The date/time of first dose of study treatment in a combination group is the earliest date/time of the first non-zero dose date/time for the study drugs in the combination.

The date/time of last dose of study treatment in a combination group is the latest date/time of the last non-zero dose date/time for the study drugs in the combination.

**Definition of baseline:**

Definition of baseline for efficacy analyses and for safety analyses

The last available assessment prior to the start of study treatment is defined as ‘baseline’ value or ‘baseline’ assessment for safety and efficacy analyses. If an assessment is planned to be performed prior to the first dose of study treatment in the protocol and the assessment is performed on the same day as the first dose of study treatment, it will be assumed that it was performed prior to study treatment administration, if assessment time point is not collected or is missing. If assessment time points are collected, the observed time point will be used to determine pre-dose on study day 1 for baseline calculation. Unscheduled assessments will be used in the determination of baseline. However, if time is missing, an unscheduled assessment on study day 1 will be considered to have been obtained after study treatment administration.

Patients who start treatment and discontinue from the study on the same day may have two different sets of data collected on study day 1 (one during study and one in the End of Treatment (EOT) visit. Data reported at the EOT visit are not eligible for baseline selection.

If a scheduled pre-dose measurement actually occurred post-dose, then the corresponding measurement will be treated and analyzed similar to an unscheduled post-dose measurement.

Definition of baseline for immunogenicity analyses

The last available assessment prior to the start of treatment with avelumab is defined as ‘baseline’ result or ‘baseline’ assessment. If an assessment is planned to be performed prior to the first dose of avelumab in the protocol and the assessment is performed on the same day as the first dose of avelumab, it will be assumed that it was performed prior to avelumab administration, if assessment time point is not collected or is missing.

**3.4.2. Baseline characteristics**

Baseline characteristics (including demographics, disease history and prior anti-cancer therapies) are described in Section 6.5.1. These baseline characteristics are not planned to be included as stratification variables or covariates in statistical models unless otherwise specified in Section 6.

**3.5. Safety Endpoints**

**3.5.1. Adverse events**

**Treatment-Emergent Adverse Events**

Treatment-emergent adverse events (TEAEs) are those events with onset dates occurring during the on-treatment period.

**On-treatment period** is defined as the time from the first dose of study treatment through minimum (30 days + last dose of study treatment, start day of new anti-cancer drug therapy – 1 day). The start day of new anti-cancer drug therapy after the first dose of study treatment is derived as outlined in Section [5.2.5](#).

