The most frequent treatment-related adverse events (TRAEs), ie, those reported for  $\geq 20\%$  of patients, and any Grade 5 TRAEs are shown in Table 1. A total of 32 (58.2%) patients had a TRAE of Grade  $\geq 3$  severity: 26 (47.3%) patients had Grade 3 TRAEs, 5 (9.1%) patients had a Grade 4 TRAE, and 1 (1.8%) patient had a Grade 5 TRAE (myocarditis). The autopsy of the patient with a Grade 5 TRAE indicated immune myocarditis.

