### **5.1. Allocation to Treatment**

At the time that a patient has signed informed consent and entered screening, the site should contact the interactive response technology (IRT) system to obtain the patient identification number.

Once a patient has met all eligibility criteria, assignment of patient enrollment number, patient enrollment, and allocation of investigational product will be managed by the IRT system. The site will need to contact the IRT system to enroll the patient and to obtain the study drug allocation information. At the time of enrollment, site personnel (study coordinator or specified designee) will be required to enter into or select information from the IRT system including, but not limited to, the user's identification and password, the protocol number, and the patient enrollment number. The IRT system will then provide a treatment assignment and dispensable unit (DU) or vial or bottle number for each investigational product to be dispensed. The IRT system will also provide a confirmation report containing the patient number and DU or vial or bottle numbers assigned. The confirmation report must be stored in the site's files.

Study treatment must be initiated preferably on the day of enrollment, but no later than 3 calendar days after enrollment.

There is a 24 hour a day, 365 days a year IRT helpdesk available for any questions or issues. The study specific IRT reference manual will provide the contact information and further details on the use of the IRT system.

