#### **8.1.4. Time Period for Collecting AE/SAE Information**

The time period for actively eliciting and collecting AEs and SAEs (“active collection period”) for each patient begins from the time the patient provides informed consent, which is obtained before the patient’s participation in the study (ie, before undergoing any study-related procedure and/or receiving investigational product), through and including a minimum of 90 calendar days after the last administration of the investigational product.

For patients who are screen failures, the active collection period ends when screen failure status is determined.

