## **9.6. Safety Analysis**

### **9.6.1. Adverse Events**

AEs will be graded by the investigator according to the CTCAE version 4.03 and coded using the Medical Dictionary for Regulatory Activities (MedDRA). The focus of AE summaries will be on Treatment Emergent Adverse Events, those with initial onset or increasing in severity after the first dose of study treatment. The number and percentage of patients who experienced any AE, SAE, treatment-related AE, and treatment-related SAE will be summarized according to worst toxicity grades.

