#### **5.3.2.2. Adverse events**

Incomplete AE-related dates will be imputed as follows:

- If the AE onset date is missing completely, then the onset date will be replaced by the start of study treatment.
- If only the day part of the AE onset date is missing, but the month and year are equal to the start of study treatment, then the AE onset date will be replaced by the start of study treatment. For example, if the AE onset date is --/JAN/2015, and study treatment start date is 15/JAN/2015, then the imputed AE onset date will be 15/JAN/2015.
- If both the day and month of the AE onset date are missing but the onset year is equal to the start of study treatment, then the onset date will be replaced by the start of study

treatment. For example, if AE onset date is --/---/2014, and study treatment start date is 19/NOV/2014, then the imputed AE onset date will be 19/NOV/2014.

- In all other cases the missing onset day or missing onset month will be replaced by 1.
- Incomplete stop date will be replaced by the last day of the month (if day is missing only), if not resulting in a date later than the date of patient's death. In the latter case the date of death will be used to impute the incomplete stop date.
- In all other cases the incomplete stop date will not be imputed. If stop date of AE is after the date of cut-off outcome of AE is ongoing at cut-off.

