#### **6.6.1. Adverse events**

Treatment-emergent adverse events (TEAEs) are those events with onset dates occurring during the on-treatment period as defined in Section 3.5.1.

All analyses described below will be based on TEAEs (started during the on-treatment period) if not otherwise specified. The AE listings will include all AEs (whether treatment-emergent or not). AEs outside the on-treatment period will be flagged in the listings.

- **Related Adverse Events:** adverse events with relationship to study treatment (as recorded on the AE eCRF page, Relationship with study treatment = Related) reported by the investigator and those of unknown relationship (ie, no answer to the question ‘Relationship with study treatment’). Related AEs are those related to any study drug (ie, at least one of the study drugs).
- **Serious Adverse Events (SAE):** serious adverse events (as recorded on the AE eCRF page, Serious Adverse Event = Yes).

- **Adverse Events Leading to Dose Reduction:** adverse events leading to dose reduction of study treatment (as recorded on the AE eCRF page, Action taken with study treatment = Dose reduced).
- **Adverse Events Leading to Interruption of Study Treatment:** adverse events leading to interruption of study treatment (as recorded on the AE eCRF page, Action taken with study treatment = Drug interrupted). The eCRF does not allow for a clear separation between interruption of an infusion and delays of administration for a parenteral drug as both are recorded using the same term on the eCRF (“Drug interrupted”). IRRs will be excluded in the analysis of AEs leading to Drug Interruption in case they only led to an interruption of the infusion.
- **Adverse Events Leading to Permanent Treatment Discontinuation:** adverse events leading to permanent discontinuation of study treatment (as recorded on the AE eCRF page, Action taken with study treatment = Drug withdrawn).
- **Adverse Events Leading to Death:** adverse event leading to death (as recorded on the AE eCRF page, Outcome = Fatal, as well as AEs of Grade 5).
- **Immune-related Adverse Events (irAE):** irAEs (as identified according to the methodology outlined in Appendix 1 for a pre-specified search list of MedDRA PTs, documented in the Safety Review Plan and finalized for analysis of the current study data prior to DB lock)

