#### **Parameters with NCI-CTC grades available:**

The laboratory toxicities will be tabulated using descriptive statistics (number of patients and percentages) during the on-treatment period. The denominator to calculate percentages for each laboratory parameter is the number of patients evaluable for CTCAE grading (ie those patients for whom a Grade 0, 1, 2, 3 or 4 can be derived).

- The shift table will summarize baseline CTCAE grade versus the worst on-treatment CTCAE grade. The highest CTCAE grade during the on-treatment period is considered as the worst grade for the summary.
- The number and percentage of patients with newly occurring or worsening laboratory abnormalities during the on-treatment period will be summarized by worst grade on-treatment (Grade 1, 2, 3, 4, Grade 3/4 and any grade (Grades 1-4)).

The above analyses apply to hematology and chemistry evaluations which can be graded per CTCAE, ie:

- **Hematology:**

Hemoglobin (HB), Leukocytes (white blood cell decreased), Lymphocytes (lymphocyte count increased/decreased), Neutrophils / Absolute Neutrophils Count (ANC) (neutrophil count decreased), Platelet Count (PLT) (platelet count decreased).

- **Serum Chemistry:**

Albumin (hypoalbuminemia), Alkaline Phosphatase (alkaline phosphatase increased), Alanine Aminotransferase (ALT) (ALT increased), Amylase (serum amylase increased), Aspartate Aminotransferase (AST) (AST increased), Total Bilirubin (blood bilirubin increased, Cholesterol (cholesterol high), Creatinine (creatinine increased), Creatine Kinase (CPK increased), Potassium (hypokalemia/ hyperkalemia), Sodium (hyponatremia/ hypernatremia), Magnesium (hypomagnesemia/hypermagnesemia), Calcium (hypocalcemia/ hypercalcemia), Glucose (hypoglycemia/hyperglycemia), Gamma Glutamyl Transferase (GGT) (GGT increased), Lipase (lipase increased), Phosphates (hypophosphatemia), Triglycerides (hypertriglyceridemia).

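### The SAP defines treatment-emergent AEs by onset date only and omits the protocol's worsening criterion, so a pre-dose AE that worsens under one record is left out of the TEAE tables

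*SAP*

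**What the plan says.** Protocol 9.6.1 puts the focus of the AE summaries on treatment-emergent events and gives two ways to qualify: "those with initial onset or increasing in severity after the first dose of study treatment".

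SAP 3.5.1 gives one: "Treatment-emergent adverse events (TEAEs) are those events with onset dates occurring during the on-treatment period". SAP 5.2.7 starts the on-treatment period at the first dose. SAP 6.6.1 repeats the onset rule and applies it throughout: "All analyses described below will be based on TEAEs (started during the on-treatment period) if not otherwise specified". The same section keeps all AEs in the listings and flags those outside the period.

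Under protocol 8.1.4 the active collection period "begins from the time the patient provides informed consent". The AE row of the Schedule of Activities is blank at screening, but its footnote refers to 8.1.4 for the collection period.

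The only worsening rule visible in the SAP is for graded laboratory tests, in 6.6.5.1: "newly occurring or worsening laboratory abnormalities during the on-treatment period".

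**The concern.** Safety and tolerability is a secondary objective, and AE severity is part of the corresponding endpoint. The TEAE tables are where most readers will look for it. An AE recorded at Grade 1 or 2 after consent and before dosing, which reaches Grade 3 on treatment, is what the protocol's second criterion is there to catch. Under the SAP, the onset date of that record falls before the on-treatment period. If the record is not split, the event appears in no TEAE count: neither the overall row, nor the Grade 3 or higher row, nor the row for its preferred term. The tables would then rest on a narrower definition than the protocol's, with no visible statement that the change was intended.

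**Working it through.** The plan gives no figure to reproduce. The check compares the two definitions, followed by a little arithmetic on size.

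**Inputs**
- Protocol rule: onset or increase in severity after first dose (9.6.1).
- SAP rule: onset date in the on-treatment period (3.5.1, 6.6.1), which starts at first dose (5.2.7).
- AE collection starts at consent (protocol 8.1.4).
- Screening is at most 28 days before enrollment (Schedule of Activities). Treatment starts "no later than 3 calendar days after enrollment" (protocol 5.1).
- About 40 patients per cohort (protocol 9.2, SAP 5.1.1).

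**Step 1: which records the two rules treat differently**
- *AE first recorded between consent and first dose, grade rises on treatment, same record.* Protocol: counted. SAP: not counted, because the onset date precedes first dose. The rules differ here.
- *Same AE, with the worsening entered as a new record that has its own on-treatment onset date.* Counted under both.
- *Symptom held only as medical history or as a baseline sign or symptom, with worsening on treatment entered as the first AE record.* Counted under both.

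Only the first case is exposed. Neither document says whether a grade increase opens a new record. SAP 6.6.1.3 shows that one preferred term can have several records with different onsets, so the second case is possible but is not stated as a rule.

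**Step 2: direction.** Within the same on-treatment period, the events that qualify by onset are a subset of those that qualify by onset or worsening. Dropping the worsening criterion can therefore only leave TEAE counts the same or lower them.

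**Step 3: length of the exposed interval.** 28 + 3 = 31 days at most, approximately, from the start of screening to first dose.

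**Step 4: size per patient.** One affected patient in a cohort of 40 is 1/40 = 0.025, or 2.5 percentage points, in any one row. This is a ceiling. The row does not move if that patient already has another event that qualifies for it. The number of affected patients is not in the documents, so no cohort total can be given.

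**The case against.** The strongest reply is that the loss is conditional and may be nil. It depends on CRF completion rules that are not in the documents. If sites open a new record whenever the grade rises, the SAP's rule captures everything the protocol's does. This stands, and it is why the point is conditional on a single record.

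The exposed group is also narrow. The Schedule of Activities lists medical history and baseline signs and symptoms separately from AEs, and nothing says they are entered on the AE page. A reader might infer that any pre-existing Grade 1 or 2 symptom that worsens is lost. The documents do not support that. Only AEs first recorded between consent and first dose are clearly exposed.

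The events are not lost from the report either. SAP 6.6.1 lists all AEs. Sections 6.6.1.2 to 6.6.1.4 list those leading to dose reduction, interruption or discontinuation, and 6.6.3 lists all SAEs. Worsening of graded laboratory tests has its own summary. The loss is from summary counts of reported AEs. This stands too.

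Three further arguments are tempting and do not hold:
- The laboratory rule does not contradict the AE rule. Laboratory grades come from measured values at baseline and on treatment, whereas AE tables use investigator-reported records.
- SAP 5.3.2.2 says "If the AE onset date is missing completely, then the onset date will be replaced by the start of study treatment". A reader might infer that this makes the net direction of error uncertain. It applies equally under either TEAE definition, so it cannot offset the missing criterion. An event with no onset date is also not known to be pre-dose.
- The 30-day end of the TEAE period and the 90-day irAE window in SAP Appendix 1 are both openly stated, and later events are listed and flagged. Extra day-90 tables or a footnote on the irAE row would be a matter of preference or labelling, not the correction of an error.

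**Conclusion.** The difference is real and can be read directly from the two definitions. No visible text restores the worsening criterion for reported AEs. Its effect runs one way, towards lower TEAE counts than the protocol definition would give, with a ceiling of 2.5 points per affected patient in any row and a floor of zero. The loss assumes that some AEs are recorded between consent and first dose, that some of them worsen on treatment, and that the worsening stays on the original record. The documents allow all three but establish only that collection begins at consent.

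A reader might try to size the effect from the earlier renal cell carcinoma study B9991002, where protocol 1.2.6 reports: "A total of 32 (58.2%) patients had a TRAE of Grade" 3 or higher. That would require an assumed number of affected patients, an assumption that every such event reaches Grade 3 and is judged related although it began before dosing, and carry-over of rates from another tumor type. The documents support none of these, so no such estimate is given.

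Nor is this a breach of the protocol. Protocol section 9 and SAP section 2 let the SAP modify the protocol's plans, and only major changes to the primary endpoint or its analysis must also go into an amendment. The SAP version history is largely redacted, so whether a reason was recorded cannot be judged. Severity is low: a definition to reconcile in a descriptive secondary summary.

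**What to change.** In SAP 3.5.1 and 6.6.1, define a TEAE as an AE whose onset, or whose increase in grade over its pre-dose grade, falls in the on-treatment period. The parenthesis in 6.6.1 that describes TEAEs as events started on treatment should be changed to match.

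If the CRF already opens a new record with a new onset date at each grade increase, keep the onset rule and say so in both places. The two definitions then agree in effect, and no programming changes.

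The cost is one sentence in two sections. The limitation of the first option is data: the pre-dose grade of each AE must be available on the CRF. If a record holds only its worst grade, on-treatment worsening cannot be derived, so the CRF structure should be checked before choosing between the two.
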